5.3 Safety follow-up of subjects who have withdrawn from the Study

Subjects who have withdrawn from the trial after treatment with the Study device for any reason will undergo ongoing monitoring of any existing adverse events until the findings of the tests related to the adverse event and required by SOCs have returned to baseline values, or until the investigator has verified that these events are no longer clinically significant.

Subjects who exhibit adverse events up to thirty days after the last visit or the last *follow-up* (whichever occurs last) will be monitored until the findings of their tests have returned to baseline values, or until the investigator has verified that the results are no longer clinically significant.

5.4 Safety follow-up of subjects who have completed the Study

All subjects with adverse events when they complete the Study will be monitored until the findings of their tests have returned to baseline values, or when no further changes are expected, or until the investigator has verified that the results are no longer clinically significant.

6. STATISTICAL PLAN

Ninety subjects will be enrolled in this study. Each subject is part of both the control group and the treatment group.

Given that each patient will both receive the treatment and will also be a control subject, both groups will contain the same number of subjects, even if some of the subjects withdraw from the study. A comparative study of the subjects' demographic data and other baseline characteristics will also not be necessary as the two groups will be perfectly superimposable.

Treatment will be administered immediately after the cleaning and any necessary debridement of the complete wound. The area of the wound that should not be treated with the EmoLED device will be duly marked and covered with different layers of sterile dressing; this facilitates treatment standardisation and uniformity, thereby limiting any variability; it will also enable the treated, untreated and adjacent areas of each subject to be coherently defined.

The aim of the statistical analysis will be to establish the efficacy of the treatment with the EmoLED device; the significance ($p<0.05$) of any difference observed in the healing process between treated and untreated areas will be evaluated. Specifically, the primary endpoint of the study is the percentage reduction of the area of the wound treated with the EmoLED device versus the wound not treated with the EmoLED device at W10.

The secondary endpoints are:

1. Treatment safety.
2. Outcomes comparison in terms of the percentage reduction of the area of the wound treated with the EmoLED device versus the wound treated with SOC only within the ten-week observational period.
3. Evaluation of difference in healing time between the two areas.
4. Pain reduction (with pre-treatment assessment on a 0-10 VAS)
5. (OPTIONAL) Depending on the patient's willingness to continue to go to the study site, the observation of any unhealed area(s) over the 10-week period can be extended until complete healing or up to 20 weeks.

Estimation of sample size

The considerations underlying the choice of the model described below were drawn from a review of the literature on leg ulcer therapies and healing dynamics as well as on past clinical experience data obtained by the sites involved in the study with the treatment in question.

The most significant finding yielded by the analysis of the clinical data in our possession is an expected 30% variability in the percentage reduction of the area of the wound at week 10. This value was confirmed by [15], where it was used to estimate the sample size. On the other hand, [16] found the standard deviation of the percentage reduction of the area of the wound to be 53% in the worst case and limited to venous ulcers only.

The analysis for the calculation of the sample size is based on:

- the clinical objective, which is represented by the percentage reduction of the area of the wound at W10
- a non-parametric statistical instrument for paired data, namely the Wilcoxon signed-rank test
- an a priori hypothesis of expected variability of 50% (conservative value)
- an expected 20% mean difference in the percentage reduction between the treated and the non-treated area
- a statistical power of 80% ($\beta=0.2$) and $\alpha=0.05$ will be considered
- a unilateral alternative hypothesis: the EmoLED treatment does not result in worsened outcome
- A correlation coefficient between percentage reductions of the treated and untreated area of 0.1, 0.3, 0.5 and 0.7
- A method for estimating the sample size based on asymptotic relative efficiency, compared to the t-test (minARE)

| | Estimate 1 | Estimate 2 | Estimate 3 | Estimate 4 |
|---|------------|------------|------------|------------|
| β | 0.2 | 0.2 | 0.2 | 0.2 |
| α | 0.05 | 0.05 | 0.05 | 0.05 |
| Diff. in % wound area reduction after 70 days | 20% | 20% | 20% | 20% |
| ρ | 0.1 | 0.3 | 0.5 | 0.7 |
| n | 83 | 65 | 47 | 29 |

The higher estimate is that relating to case 1, whose sample size is 83 subjects, which served as the basis for the choice of the number of subjects to be recruited, taking into account possible loss of subjects during treatment.

Statistical analysis of the primary endpoint.

A Wilcoxon signed-rank test with a significance level of 0.05 will be performed to evaluate the efficacy of use of the device. This test allows paired data to be handled and is robust enough to evaluate variability in observation distribution. A population analysis, as well as a per-protocol analysis (PP), will be performed for the subjects who complete the study.

Statistical analysis of secondary endpoints.

1. Treatment safety.

Adverse event reports will be collected, analysed and managed according to the criteria indicated in 5.2. The most appropriate statistical instrument will be chosen for analysis based on the number and type of adverse events reported.

2. Outcomes comparison as percentage reduction of the area of the wound treated with the EmoLED device versus the wound treated with SOC alone during the 10-week observation period.

Both the areas of the wound treated with the EmoLED device and those not treated with the EmoLED device, as measured on the required observation days, will be considered. A statistical analysis of paired data will be

performed using repeated measurements. In particular, both a comparison of the measurements obtained on different days, separately, and an analysis that will take into account the global trend over the observation period, will be performed.

Tests for data paired to pairs of measurements obtained on different observation days will be performed in the first case. These tests will be applied separately to the various days, evaluating any significant differences in both treated and untreated areas. The adopted statistical test will be either a parametric (t-test) or a non-parametric test (Wilcoxon signed-rank test) depending on the observed data distribution. The statistical significance will be corrected for multiple comparisons (e.g., given the possibility of a positive correlation between the identified measurements, Benjamini-Hochberg correction will be considered).

In the second case, the area under the curve (AUC) will be evaluated for each subject and in each area in order to obtain information on possible differences between changes in the treated and untreated areas of the wound. Either parametric or non-parametric paired data tests (depending on parameter distribution) will be performed in order to evaluate any differences in the trends of this parameter summarising the healing dynamics both in the treated and untreated areas.

The mean value observed in the remaining subjects will be used for both approaches if there is any missing data. A sensitivity analysis will be performed using both the best value and the worst value observed in the subjects.

3. Evaluation of the difference in healing time between the two areas.

A survival analysis will be performed based on the Akritas test applied to the Kaplan-Meier curve. This type of analysis is used to evaluate the time from observation to the event of interest (time-to-event). In particular, in this case, the event will be a percentage reduction of the area of the wound of $\geq 70\%$ at W10. This approach will allow both paired data and the possibility that some of the subjects may be non-adherent to the protocol and withdraw from the study to be managed. A curve will be constructed for each group, each corresponding to the analysis of the two areas, both that treated with the EmoLED device and that not treated with the EmoLED device. The Akritas test is based on a transformation into ranked "survival" times, understood as time to event of interest (time-to-event). In particular, in this case, the event will be a percentage reduction of the area of the wound of at least 70% at W10. Ranked observations will be transformed according to a model that takes into account the possibility that they may be truncated or censored.

4. Pain reduction (pre-treatment assessment on a 0-10 VAS).

A non-parametric analysis will be performed using the Friedman test, which can be considered the non-parametric equivalent of the ANOVA test for repeated measurements.

5. (OPTIONAL) Depending on the patient's willingness to continue to go to the study site, the observation of any unhealed area(s) over the 10-week period can be extended until complete healing or up to 20 weeks.

The analysis will be performed as for endpoint 2.

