2. STUDY OBJECTIVES

The aim of this clinical study is to determine whether the proposed treatment represents a valid and significant treatment for ulcers by evaluating the percentage reduction of the area of the wound over a 10-week observation period and comparing the reduction of the area of the wound (or part of the wound), both on the same patient and within the entire group, treated with the EmoLED device, versus the control wound (or part of the wound) treated with a standard method. Over the 10-week period following their recruitment, the patients will continue to take their usual topical therapy and attend the weekly visits. Patients will be monitored:

- until healing, if this occurs before week 10,
- until week 10 in the event of incomplete healing.

Additionally, given that the device does not yet have CE marking, reports and assessments on the safety and usability of the device will be complied by the medical staff during the study.

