If, at recruitment, a patient has more than one wound with a **diameter greater than 5 cm**, all wounds will be divided into two halves along the longest side and treated as described above.

After treatment with the EmoLED device, the wound will be dressed with a hydrofibre dressing. If clinical signs of infection occur, the wound will be dressed with a hydrofibre dressing with silver. The limb will then be bandaged with a compression bandage.

4.1.2 Standard treatment and data recording.

Any wounds or parts of wounds that are not treated with the EmoLED device will be medicated using the standard treatment consisting of a hydrofibre dressing or hydrofibre dressing with silver (as described above) and compression therapy. Ultimately, the treatment differs only for the fact that the EmoLED device is used in accordance with the procedure described above, while the rest of the treatment remains unchanged.

Following enrolment and the signing of the Informed Consent Form, the pertinent data from each patient will be recorded in the respective Case Report Form according to the following schedule: W0 (Week 0: enrolment and first treatment), W1, W2, W3 ... to W10, as per the routine visits over the 10-week period from enrolment.

Patients may miss a maximum of two non-consecutive follow-up visits over the 10-week period, starting from visit 5. Patients will be excluded from the study if consecutive visits are missed.

The parameters used to define the study outcomes will be based on:

- photographic images of the wounds treated with the EmoLED device as well as of control wounds
- Case Report Form completed by the doctor during the visits.

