4.2 Primary endpoint of the study

The primary endpoint of the study will be a comparison of the outcomes in terms of percentage reduction of the area of the wound treated with the EmoLED device versus the wound treated with SOC at W10, both the difference in the individual patient and within the entire group of 90 recruited patients.

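### The primary analysis, read literally, is confined to completers and drops patients who miss consecutive visits, against an endpoint set on all 90 recruited; the primary test has no missing-data rule

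*Combined protocol and SAP*

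**What the plan says.** Section 4.2 defines the primary endpoint as the percentage area reduction at W10, device against standard care, taking "both the difference in the individual patient and within the entire group of 90 recruited patients".

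Section 6, under the analysis of the primary endpoint, specifies a Wilcoxon signed-rank test and then states: "A population analysis, as well as a per-protocol analysis (PP), will be performed for the subjects who complete the study". Read literally, the closing words "will be performed for the subjects who complete the study" apply to both analyses. It defines neither the population analysis nor completion, and does not say which of the two analyses is primary.

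Section 4.1.2 sets the attendance rule: "Patients may miss a maximum of two non-consecutive follow-up visits over the 10-week period, starting from visit 5". It continues: "Patients will be excluded from the study if consecutive visits are missed".

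Section 2 adds that monitoring runs "until healing, if this occurs before week 10". The plan does not say whether an area that closed early enters the W10 comparison as a 100% reduction, or whether such a patient counts as having completed.

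The only imputation rule is given under secondary endpoint 2: "The mean value observed in the remaining subjects will be used for both approaches if there is any missing data". A sensitivity analysis with best and worst values follows it. Neither is extended to the primary test.

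**The concern.** The endpoint names one set of patients and the analysis, on its literal wording, uses another. The visit rule widens the gap. The primary endpoint needs only the W0 and W10 areas, yet a patient who misses two visits in a row is removed even if the W10 photograph could be obtained.

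The usual reassurance in a within-patient design is that both areas leave together, so the groups stay equal in size; section 6 makes this point. Equal size does not mean absence of bias. The paired mean is protected only if leaving is unrelated to how one area does relative to the other. The documents describe no masking, so a patient can see how the treated area is doing, and that may affect attendance. At stake are the estimate, the false-positive rate and, to a lesser extent, power.

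**Working it through.** **1. The plan's own sample size.** Inputs from section 6: difference 20 points, SD 50 per area, correlation ρ 0.1 to 0.7, one-sided α 0.05, power 80%, signed-rank test sized by minARE (0.864).

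- SD of the paired difference at ρ = 0.1: 50 × √(2 × (1 − 0.1)) = 67.08.
- Standardised difference: 20 / 67.08 = 0.298.
- Power comes from a noncentral t distribution with effective size 0.864n, degrees of freedom 0.864n − 1 and noncentrality 0.298 × √(0.864n).
- The smallest n with at least 80% power is 83. The same steps give 65, 47 and 29 at ρ = 0.3, 0.5 and 0.7.

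All four figures match the plan's table, so the sizing is not at fault.

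**2. Power cost of loss (ρ = 0.1).** The margin is 90 − 83 = 7 patients, or 7/90 = 7.8%.

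| Analysed | Loss | Power |
|---|---|---|
| 90 | 0% | 83.2% |
| 83 | 7.8% | 80.4% |
| 81 | 10% | 79.5% |
| 72 | 20% | 75.2% |

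**3. Bias from informative loss.** The plan gives no drop-out rate or reasons, so the following is assumed: no true effect, 90 patients, normally distributed reductions with SD 50, and loss following a logistic model in which the log-odds rise by 1 (odds by e¹ ≈ 2.7) per SD of poorer response in the area that drives it. The test is the one-sided signed-rank test at 0.05.

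| Loss driven by | ρ | Loss | Shift (points) | False positives |
|---|---|---|---|---|
| Treated area | 0.1 | 10% to 16% | +4.1 to +6.2 | 14% to 20% |
| Treated area | 0.5 | 10% to 16% | +2.1 to +3.6 | 10% to 15% |
| Treated area | 0.7 | 10% to 16% | +1.3 to +2.0 | 9% to 11% |
| Control area | 0.1 | 10% | −4.3 | 1.7% |
| Patient's average healing | 0.1 | 10% | about 0 | about nominal |

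Repeat runs differ by about one percentage point in the false-positive rate. With a weaker link (odds 1.6-fold per SD, 11% loss, ρ = 0.1), the shift is about +2 points with about 8% false positives.

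The pattern across ρ can be checked by hand. If loss depends on the treated area alone and that area's mean among completers moves by δ, the control mean moves by ρδ, and the paired difference by (1 − ρ)δ. At 10% loss and ρ = 0.1, δ = 4.1 / 0.9 ≈ 4.6. At ρ = 0.7 the predicted shift is 0.3 × 4.6 ≈ 1.4, close to the simulated +1.3.

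The point shifts scale with the SD. At the 30% that section 6 reports from the sponsor's own data they are multiplied by 30/50 = 0.6, so +4.1 to +6.2 becomes about +2.5 to +3.7. The false-positive rates do not change, because the signed-rank test is unaffected by scale.

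**4. Whether the endpoint 2 imputation would help.** Suppose k patients complete with mean difference D̄, and the other 90 − k have both areas filled in with the completers' means. Each imputed pair then has difference D̄, and the overall mean is [kD̄ + (90 − k)D̄] / 90 = D̄. The completers' bias is carried over in full, and the imputed values are treated as if they had been observed.

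**The case against.** The strongest reply is that the section 6 sentence can be read more loosely, with the population analysis on everyone and only the per-protocol analysis on completers. Naming two analyses suggests two sets, and on that reading sections 4.2 and 6 agree. This reading is possible. It does not close the gap: the terms are undefined, and a patient without a W10 area cannot enter a signed-rank test unless a missing-data rule says how.

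A reader might infer that the plan contains no all-patients analysis at all. The documents do not support that. Secondary endpoint 2 includes paired tests by observation day, which can include W10, with imputation and best/worst-value sensitivity analyses. The healing-time analysis was chosen partly so that withdrawals can be handled. The gap concerns the primary test.

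A reader might also infer that the population and per-protocol sets become identical. That does not follow. A completer can still breach the visit rule, for instance by missing a visit before visit 5 or three non-consecutive visits, and exclusion is stated only for consecutive misses.

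It is also fair to say that ρ = 0.1 and SD 50 are the inputs that give the largest shifts, and that the seven-patient margin applies only at ρ = 0.1 (the plan's table needs 65 patients at ρ = 0.3). Both points stand, which is why the results are shown across ρ. The false-positive inflation shrinks as ρ rises but does not disappear.

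**Conclusion.** The concern holds as an unreconciled conflict between sections 4.1.2, 4.2 and 6, together with a missing rule for the primary test. Data that could be collected are discarded under a stated rule.

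It would go too far to say that the result will be biased towards the device. The documents give no reasons for loss. Under the assumed strong link to the treated area, the shift is about +4 to +6 points at ρ = 0.1 and +1 to +2 at ρ = 0.7, against a planned effect of 20. It reverses if the control area drives loss, and vanishes if loss follows overall healing. The power cost is modest, at 83.2% with 90 analysed against 79.5% with 81. The reasons to act are the ambiguity and the possible bias. The change should be made. Confidence is high that the wording conflicts and that a primary missing-data rule is absent; the size of any bias depends on the assumed mechanism.

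**What to change.** Reconcile sections 4.1.2, 4.2 and 6 as follows.

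- Define the primary set as all enrolled patients with a W0 area for both members of the pair, and name the analysis of that set as primary.
- Keep patients who miss consecutive visits in follow-up for the W10 photograph, and remove them only from the per-protocol set. Define completion.
- Count an area that closed before W10 as a 100% reduction.
- For a missing W10 area, name a method that uses that patient's own weekly areas, for example multiple imputation from the weekly series of both areas. Add sensitivity analyses that include a worst case for the treated area.
- Keep per-protocol as secondary.

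The cost is protocol and analysis-plan wording, plus a W10 photograph for each patient who would otherwise be dropped. The downside is a somewhat noisier estimate that includes less adherent patients. Whether treatment continues after missed visits is a clinical matter outside this point.

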3.1 Inclusion criteria

- Subjects with venous, arterial or mixed skin ulcers and surgical wound dehiscence (18), (19);
- Presence of multiple similar wounds or one wound measuring² at least 5 cm;
- Men and women ≥ 18 years of age;
- Patients must be able to understand the aims of the Clinical Study and provide their informed consent in writing;
- Chronicity of the wound: at least 8 weeks.

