4. STUDY DESIGN

4.1 General design

This clinical study will be a multicentre, prospective, controlled study, whose aim is to evaluate the clinical efficacy of a battery-powered portable device that uses blue LEDs.

As described in greater detail in the statistical analysis section, at least a 20% difference between treated and untreated wounds is expected to be observed in the same patient within the specified observation period.

For safety, the operator will be equipped with UV protection glasses. The housing of the device is made of biocompatible material that can be disinfected with detergents commonly used in hospitals in order to prevent contamination.

The device passed all safety tests (electrical, electromagnetic and photobiological) required by current regulations on medical devices, as well as a precise risk and usability analysis, and was found to be suited to the intended use.

The treatment, which is provided in addition to the patient's standard therapy, will be performed at each visit for 60 seconds on each 5-cm diameter sub-area of the selected wound or part of it.

Therefore, for multiple wounds, one will be treated with the EmoLED device and one will be selected as a control wound; very large wounds will be divided into two halves and one of the two will be the control wound. This will reduce any variability associated with randomised clinical trials (RCTs) on skin ulcer conditions.

4.1.1 Selection of the treatment area.

All wounds will be cleaned with saline solution and, if there is slough/black eschar, surgical debridement will be performed using a scalpel. Only at this point will treatment with the EmoLED device take place.

If a patient has more than one wound and all wounds at enrolment are found to have a **diameter of less than 5 cm**, the worst of the wounds will be treated entirely with the EmoLED device, whereas the others will serve as control wounds. Progression of all wounds will be evaluated over the ten-week study duration.

By contrast, if a wound at recruitment has a **diameter greater than 5 cm**, the wound will be divided into two halves along the longest side, and only one of the two halves will be treated. The other half of the wound will be dressed with a multi-layered sterile dressing. The division line between the two halves of the wound will be marked with a permanent marker, which will be reapplied at each visit, or whenever it begins to fade, to prevent loss of the reference marks.

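### Endpoint 2 leaves the AUC's scale and post-closure values undefined, and read literally its mean-imputation rule marks down areas that close early

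*Combined protocol and SAP*

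**What the plan says.** All references are to the combined protocol and SAP.

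- **Endpoint 2 title (Section 6, secondary endpoints):** "Outcomes comparison as percentage reduction of the area of the wound treated with the EmoLED device versus the wound treated with SOC alone".
- **Data used (same place):** the treated and untreated areas, "as measured on the required observation days, will be considered".
- **AUC (same place):** "the area under the curve (AUC) will be evaluated for each subject and in each area". The plotted variable, the limits of integration and the value after closure are not stated. The stated aim is to learn whether the two areas change differently.
- **Missing data (same place):** for both the weekly tests and the AUC, a missing value is replaced by the mean of the remaining subjects. Sensitivity analyses use the best and the worst observed values. Healed areas are not mentioned.
- **Follow-up:** Section 2 has patients monitored "until healing, if this occurs before week 10". The centralised database text in Section 3.3 counts healed patients among those who leave the study. Section 4.1.1, for patients with several wounds, has all wounds evaluated over the ten weeks.
- **Allocation (Section 4.1.1):** when all wounds are under 5 cm, "the worst of the wounds will be treated entirely with the EmoLED device, whereas the others will serve as control wounds". Wounds over 5 cm are halved. Section 3.1 asks for "Presence of multiple similar wounds" without a size tolerance.

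**The concern.** The AUC is the plan's only single-number summary of the healing course, and the optional 20-week extension reuses the endpoint 2 analysis. Its result depends on two choices that the plan leaves open.

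The first is the value of an area after it closes. Once a patient has healed and left, no later areas are measured. The only stated rule for absent values is the mean of the subjects still followed, who are disproportionately those not yet healed. The plan would then swap a known outcome, complete closure, for a poorer one. The areas that did best would lose most.

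The second is the scale. On raw area, the AUC is proportional to starting size as well as to healing. Where the treated wound is chosen by rule, a systematic size difference would pass straight into the paired comparison. Section 6 calls a baseline comparison unnecessary, so no planned check would show it.

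**Working it through.** **The plan's own figures.** The plan gives none for the AUC. The primary-endpoint sample size reproduces. With SD 50, ρ = 0.1, a difference of 20, one-sided α = 0.05 and 80% power, the SD of the difference is 50·√(2·0.9) = 67.1. The paired t-test then needs 71, and 71/0.864 = 82.2, rounded up to the stated 83. The figures 65, 47 and 29 also reproduce. None of them involves the AUC.

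**1. Direction of the imputation effect.** Percentage reduction cannot exceed 100. A mean over remaining subjects is therefore at most 100%, and is lower unless every remaining area has closed. Substituting it for a closed area can only lower that area's value. On raw area the true value is 0 and the fill can only raise it. This needs no assumption about healing paths.

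**2. Size, by illustration.** Assumptions: an area closes linearly at week *h*, visits are weekly, the trapezoidal rule applies, and the remaining subjects' mean rises by *s* points a week. The documents give no path, so *s* = 4, 6 and 8 (40%, 60% and 80% at W10) are shown.

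- 100% carried to W10: AUC = 50*h* + 100(10 − *h*). For *h* = 4: 200 + 600 = 800.
- Filled with the mean, *h* = 4: 200 + (100 + 5*s*)/2 + *s*(5.5 + 6.5 + 7.5 + 8.5 + 9.5) = 250 + 40*s*. For *s* = 6 this is 490.

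| Closure | 100% carried | Filled, s = 4 | Filled, s = 6 | Filled, s = 8 |
|---|---|---|---|---|
| Week 4 | 800 | 410 | 490 | 570 |
| Week 5 | 750 | 440 | 510 | 580 |
| Week 6 | 700 | 466 | 524 | 582 |

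In each filled column the order is reversed: the earliest closer scores lowest. The W10 value falls from 100% to 40%, 60% or 80%.

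**3. Effect on one pair.** Take *s* = 6, a treated area closing at week 4, and a control reaching 60% at W10 (AUC 0.5·10·60 = 300). The true AUC difference is 800 − 300 = 500; after filling it is 490 − 300 = 190. At W10 the true difference is 100 − 60 = 40 points; after filling it is 60 − 60 = 0.

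**4. Raw-area reading.** Suppose both wounds heal linearly to 60% at W10, from 12 cm² (treated) and 10 cm² (control). Each fraction remaining integrates to 10 − 0.5·10·0.6 = 7.0 weeks, so the AUCs are 84 and 70 cm²-weeks. Their ratio is the baseline ratio, 1.2. Now give the treated wound the plan's 20-point advantage (60% against 40%). The integrals are 7.0 and 8.0, so the AUCs tie at a baseline ratio of 8/7 = 1.14. At 1.2 the control looks better (84 against 80). If the treated wound were the smaller one, the error would run the other way. On percentage reduction, equal healing gives 300 against 300 at any baseline ratio.

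**The case against.** **Percentage reduction is the more natural reading.** The title says so, the stated purpose is to compare changes, and the phrase about measured areas may only name the source data. This stands: raw area is the weaker reading, and the plan is ambiguous rather than wrong on scale.

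**A reader might infer that the device is put at a disadvantage because the treated wound is the larger one.** The documents do not support this. Worst is undefined and could refer to depth, tissue bed or duration. Section 3.1 asks for similar wounds, and wounds over 5 cm are halved, so their starting areas are roughly matched. A rejection rate could be simulated, but it would be driven by the share of multi-wound patients, the size excess and the spread of healing rates. The documents give none of these, so no rate is offered.

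**A reader might also infer that the curve is simply cut at closure.** An area closing at week 6 would then score 0.5·6·100 = 300, no better than one reaching 60% at W10. No passage prescribes that cut; the stated rule fills missing values.

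**The two problems do not add up to one bias.** On raw area, stopping at closure costs nothing in itself, because the area is then 0. On percentage reduction, baseline size is normalised out. This also stands. Only the imputation rule can act on either scale.

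**Follow-up may continue until both areas close.** Section 2 speaks of patients, not areas, and Section 4.1.1 has all wounds followed for ten weeks. If so, the first area to close is still seen at 100%, and the problem shrinks to visits after both have closed. There the true difference is 0. If means are taken separately for treated and control areas, which the plan does not say, the fill would insert the group difference instead.

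**A sensible analyst would enter 100% anyway.** Probably, but the plan does not say so and its rule covers any missing data. The best-value sensitivity analysis could give a closed area 100%, but it would give the same value to every drop-out.

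**Conclusion.** The concern holds in a limited form. The AUC lacks a defined scale, window and post-closure value. Taken literally, the follow-up and imputation rules together replace a closed area's 100% with a lower mean, in the AUC and in the weekly tests. That this understates early closure follows from the rules, provided post-closure visits are treated as missing. The size rests on assumed linear paths: for week-4 closure, 410 to 570 instead of 800 %-weeks, with 490 on the 6-points-a-week path.

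The raw-area problem is conditional. It arises only if raw areas are used and the treated wounds differ systematically in starting size. It is confined mainly to patients whose wounds are all under 5 cm, and its size and direction are unknown.

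This affects one secondary endpoint and its optional extension. The AUC plays no part in the primary W10 comparison or the sample size. It is worth settling before data are seen, because choosing the scale or the post-closure value afterwards could change the result.

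**What to change.** Amend endpoint 2 in Section 6 as follows.

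1. Define the outcome for both the weekly tests and the AUC as percentage reduction from each area's own W0 area.
2. Define the AUC by the trapezoidal rule over a fixed W0-W10 window, compared within patient.
3. Carry 100% forward from closure to W10 for any area no longer measured. This assumes that a closed area stays closed.
4. Exempt healed areas from the mean, best-value and worst-value imputation, and keep those rules for values that are truly missing.
5. Reconcile Section 2 with Section 4.1.1 on whether follow-up continues for the other area once one has closed.

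State how the same rules apply to the optional extension. The cost is a few sentences, with no new data and no change to the sample size.
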